acid (UDCA) could enhance the bile synthesis by CYP7A1 altering the gut microbiota population. UDCA also has other beneficial effects, such as anticholestatic, antifibrotic, antiproliferative, and anti-inflammatory [12-14].

In retrospective studies, statins appear to be safe in patients with compensated cirrhosis, and evidence suggests that they may significantly reduce fibrosis (HR:0.56, p<0.0001)[15]. Preclinical data from studies performed on in vitro and in vivo animal models shed light on favorable effects of statins on endothelial function, angiogenesis, PHTN, and fibrosis. Suggested mechanisms involve regulation of KLF2, eNOS, thrombomodulin, and C-natriuretic peptide. Animal studies evidence suggests that the administration of fluvastatin, lovastatin, and simvastatin to primary rat hepatocytes and human hepatoma cell line inhibits the paracrine activation of HSCs [16], reduces HSC turnover and activity [17,18]. Moreover, Nature (2020) reported statin therapy is associated with lower prevalence of gut microbiota dysbiosis. [19]

The combination of ursodeoxycholic acid and statins is safe in human experiments, and the combination of the two has also proved to have a synergistic effect on the reduction of bile cholesterol levels [20], but there is no research on improving fibrosis makers or improving intestinal flora.

The goal of the current study was to evaluate our hypothesis model of pathogenesis of chronic inflammation of liver cirrhosis. We hypothesized that an adverse microbiome would exacerbate the histopathological severity of liver induced by CCL4 in a germ-free mice model. We transplanted these mice with human fecal samples from healthy controls, or liver cirrhosis treated with statin, or UDCA. The clinical trial mainly explores whether single statin or combined ursodeoxycholic acid can reduce liver fibrosis indicators, inflammatory cytokines and intestinal flora imbalance in patients with liver cirrhosis who have been cured of chronic hepatitis C or non-viral load hepatitis B.

Patients and assessments- Study design

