We expect to enroll 120 stable patients who have achieved sustained viral response (SVR) (ie, viral eradication) after hepatitis C treatment for 6 months, or non-viral load hepatitis B for 6 months, who have been diagnosed with primary cirrhosis (FIB-4 \geq 3.25) and met the Baveno VII criteria (liver stiffness measurement [LSM] \geq 25 kPa) and exclude it (LSM <15 kPa and platelet count [PLT] \geq 150 \times 10⁹/L) were used. Grey zones were classified into two groups: (high – LSM between 20–25 kPa and PLT <150 \times 10⁹/L, or LSM between 15–20 kPa and PLT <110 \times 10⁹/L, or low – defined as the remaining patients within the grey zone) [27]. **Exclusion conditions:** already taking statins, diabetes, liver cancer, alcoholic liver, moderate to severe fatty liver, liver decompensation (jaundice, ascites, esophagogastric varices, history of hepatic coma), chronic kidney disease, antibiotic use within three months and gastric ulcer medication(such as PPIs). Randomly divided into three groups: **Group 1:** control group (n =

30), Group 2: treatment group (ursodeoxy Cholic acid (UDCA) (10mg/kg/day) (n = 30), Group 3: treatment group (simvastatin 40mg) (n = 30), Group 4: treatment group (simvastatin 40mg/day + ursodeoxy Cholic acid (UDCA) (10mg/kg/day) (n = 30). Fecal bile acid content and fecal flora, skin bile acid profile, cytokine markers, biochemical fibrosis biomarker were collected at the test base point and six months after treatment. In addition, patients who achieved virus eradication without liver cirrhosis (FIB-4 < 1.45, n=30) collected the content of fecal bile acid, fecal flora, skin bile acid, and inflammatory cytokines were collected at the test base point index, biochemical fibrosis biomarkers. Analysis of flora: 16S ribosomal RNA gene sequence analysis from the patient's fecal tube. Analysis of total fecal bile acid: LC-MS/MS system analysis. Skin bile acid profile:Desorption-Electrospray Ionization Mass Spectrometry (TD-ESI/MS).

Block randomization

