Patients (n=120) were distributed on one block with 8 numbers and each group contained two numbers (1, 2, 3, 4). The admitted patients who were eligible for inclusion were given numbers in the order; number 1 was allocated to (control group) as the study group, patients who carried number 2 was allocated to (UDCA group),patients who carried number 3 was allocated to (simvastatin group), and number 4 was allocated to (simvastatin plus UDCA group). Therefore, the control and three interventional groups were randomized into 1:1:1:1.

Stool sample preparation and microbiota analysis

Bile juice and biliary stents samples will be collected in separate sterile containers containing 2mL of RNA later and will be stored at room temperature. The samples will be transferred to the laboratory within 12 h, stored at 4°C, and used for extracting DNA within few weeks. Preliminary experiments will confirm that the bacterial composition data does not change in four weeks under the storage conditions used. Genomic DNA will be isolated from stool samples using the CTAB/SDS methods (Novogene Laboratories) following the manufacturer's protocol. All microbial community DNA samples will be analyzed for V4 variable region of bacterial 16S ribosomal RNA gene using PCR primers 515F and 806R. The PCR products will be separated by 2% agarose gel electrophoresis. Samples with bright main strip between 400-450bp will be chosen for further experiments. PCR product will be mixed in equidensity ratios. Then, mixture PCR products will be purified with Qiagen Gel Extraction Kit (Qiagen, Germany). Sequencing libraries will be generated using TruSeq DNA PCR-Free sample Preparation Kit (Illumina, USA) following manufacturer's recommendations and index codes will be added. The library quality will be assessed on the Qubit® 2.0 Fluorometer (Thermo Scientific) and Agilent Bioanalyzer 2100 system. At last, the library will be sequenced on an IlluminaHiSeq2500 platform and 250 bp paired-end reads will be generated.

Fecal bile acid profile [20].

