Secondary end points: 1. Cirrhosis dysbiosis ratio (CDR), the ratio of autochthonous good bacteria (e.g. Lachnospiraceae, Ruminococcaceae and Clostridiales) to non-autochthonous/ pathogenic bacteria (e.g. Enterobacteriaceae and Streptococcaceae). 2. Total stool bile acid, Secondary and primary bile acid ratio. 3. Serum inflammation peptides (IL-6, IL-8, IL-10, and TNF-a)

Sample size : Till now, there was no prospective data to support the evaluation the sample size of study in the liver fibrosis deminition after the administrations of stain and UDCA. Prior data [24]may indicate the effect of 40 mg simvastatin versus placebo on hepatic portal pressure was studied over a period of 3 months. A significant decrease in HVPG (-15%) was noted in the experimental group versus no change in the placebo group. The study included 24 cases in each study arm. Therefore, we plan to enroll 30 participants in each arm.

Safety

Initial dose of study drug is 20 mg which can be increased to 40 mg after 4 weeks if the participant does not develop side effects. Creatine kinase and standard biochemistry including liver enzymes are measured for safety reasons after 2 weeks, to rule out myositis and liver damage. Side effects and events are consecutively registered throughout the trial. Safety of statins in chronic liver disease has been assessed in only a few clinical trials, but reviews of observational studies report high safety and low risk of adverse events, even significantly lower the all-cause mortality [25,26]

Statistical analysis:

Risks are reported as IRRs along with their 95% confidence intervals and P values. For subgroup analyses according to sample characteristics, P values for interaction also are assessed. The cumulative proportion of patients developing liver fibrosis events during follow-up is estimated by life table methods and log-rank tests were reported. P values are 2-sided, and values of .05 or less are considered statistically significant. All statistical analyses are performed using SAS version 9.1 (SAS Institute Inc).

Limitation 1:

If post treated human feces contain the trace level of drug, the hypothesis that it is caused by microorganisms alone does not hold. We will check the post treated human feces by the TD-ESI (LTQ)for simvastatin (Formula: $C_{25}H_{38}O_5$, Exact mass: 418.57 Da),and Ursodeoxycholic acid (UDCA)(Formula : $C_{24}H_{40}O_4$. Exact mass : 392.29 Da). The pre-test was performed by TD-ESI (LTQ) as followed figures.

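### One unstratified block sequence for cured hepatitis C and hepatitis B leaves the virus mix of the arms to chance; a second list would limit it cheaply

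*Protocol*

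**What the plan says.** The study design section admits two kinds of patient: those "who have achieved sustained viral response (SVR) (ie, viral eradication) after hepatitis C treatment for 6 months", "or non-viral load hepatitis B for 6 months". The closing paragraph of the background treats them as one population, namely "patients with liver cirrhosis who have been cured of chronic hepatitis C or non-viral load hepatitis B". Neither the expected share of each virus nor a cap on either is given.

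The Block randomization section covers all 120 patients with blocks of 8 in which each arm holds two numbers: "Patients (n=120) were distributed on one block with 8 numbers and each group contained two numbers (1, 2, 3, 4"). On the order of allocation it says: "The admitted patients who were eligible for inclusion were given numbers in the order". It concludes that "the control and three interventional groups were randomized into 1:1:1:1". No stratification factor is named. The Sample size section gives the arm size: "we plan to enroll 30 participants in each arm". The Statistical analysis section does not mention virus.

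**The concern.** Virus type is the one division written into the eligibility rule, and it is known for every patient before allocation. One virus has been eradicated; the other is present without detectable load. It is plausible, though the protocol gives no figure, that the two groups follow different six-month courses in the primary markers (TGF-β1, type IV collagen, hyaluronic acid, FIB-4) and in the secondary cytokines.

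A single block sequence equalises the number of patients per arm but does nothing for the mix of viruses within an arm. If virus predicts change, there are two consequences. A chance gap in mix moves an unadjusted contrast by the gap times the difference in course. Variation between the viruses also stays in the error term if virus is left out of the comparison. All three active arms are compared with the same 30 controls, so an unusual mix in the control arm affects every contrast at once.

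**Working it through.** **Inputs from the protocol.** 120 patients, blocks of 8 with two numbers per arm, allocation 1:1:1:1, 30 per arm, two-sided 0.05.

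**Assumptions.** The share p of the minority virus is not stated, so 10% to 50% is shown. The difference d between viruses in six-month change is not stated, so 0.3, 0.5 and 0.8 SD are shown, where SD is the within-virus SD. The order within each block is taken to be randomly permuted, which the protocol's wording does not make clear.

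**1. The plan's own figure.** 120/8 = 15 complete blocks; 15 × 2 = 30 per arm. This reproduces.

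**2. Imbalance under the single sequence.** The SD of the difference in share between two arms is √(2p(1−p)/30). At p = 0.5 this is √(0.5/30) = 12.9 points; at p = 0.1 it is √(0.18/30) = 7.7 points.

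A 20-point gap is 6 patients of 30. For one given active arm, the exact binomial probability of a gap that large is 15.5% at 50:50 and 12.0% at 70:30. For at least one of three active arms against the shared control, a simulation of 40,000 trials per setting gives:

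| Minority share | 5 or more patients (16.7 points) | 6 or more patients (20 points) |
|---|---|---|
| 10% | 13% | 5% |
| 20% | 33% | 18% |
| 30% | 44% | 28% |
| 40% | 49% | 33% |
| 50% | 51% | 35% |

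The simulated SDs (7.8 to 13.0 points) agree with the formula.

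**3. What a 20-point gap does to an unadjusted contrast.** The standard error is √(2/30) = 0.258 SD. The shift is 0.20 × d.

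| d (assumed) | Shift | Shift / SE | Rejection rate under the null, given this gap |
|---|---|---|---|
| 0.3 | 0.06 SD | 0.23 | 5.6% |
| 0.5 | 0.10 SD | 0.39 | 6.7% |
| 0.8 | 0.16 SD | 0.62 | 9.5% |

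The last column is conditional on the gap. Averaged over all allocations, the error rate stays at its nominal level.

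**4. Precision lost if virus is left out.** The SE is multiplied by √(1 + p(1−p)d²). At p = 0.5 this is √1.0225 = 1.011, √1.0625 = 1.031 and √1.16 = 1.077, so about 1%, 3% and 8%. A contrast with 80.0% power when there is no virus effect would have about 79%, 78% and 74%. The loss is smaller when the mix is less even: at p = 0.2 and d = 0.5 it is √1.04 = 1.020, or 2%.

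**5. Separate lists per virus.** Complete blocks are balanced, so only the last, incomplete block of each list can cause a difference, and each arm has at most two numbers in it. An active arm and control therefore differ by at most 2 patients of either virus, and 2/30 = 6.7 points. Simulation gave the same maximum and no gap of 10 points at any p. The SD of the difference in share falls from 7.8–13.0 to 2.0–2.6 points.

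**6. Cost in arm size.** If both lists end in an incomplete block, the complete blocks hold 112 patients, 28 per arm, and each arm gains 0 to 4 of the last 8. Arms therefore run from 28 to 32. A difference detectable with 80% power at 30 v 30 is (1.960 + 0.842) × 0.258 = 0.723 SD. At 28 v 32 the SE is √(1/28 + 1/32) = 0.259 and power is 79.8%. A contrast in which both arms fall short loses more: at 29 v 29 the SE is √(2/29) = 0.263 and power 78.7%; at 28 v 28 the SE is √(2/28) = 0.267 and power 77.2%. The 28 v 28 case is very rare. Both lists must stop at half a block and both halves must miss the same two arms, which has probability (1/70)² = 1/4,900 for a given pair even when both lists do stop there. Other contrasts gain when one loses, since the total stays at 120.

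**The case against.** The strongest reply is that nothing here is an error. Unstratified permuted blocks are a valid design, and chance imbalance is already reflected in the standard error. Quoting the shift only for trials with a 20-point gap can make ordinary sampling variation look like bias. This stands. A reader might infer that the single list biases the trial or inflates its false-positive rate; the protocol's design does neither.

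Second, the harm depends on two quantities that the protocol does not give. Entry is limited to stable patients with six months of viral response or absent viral load, which may narrow any difference in course. With no virus effect there is no harm, and with a 10% minority share a large gap is uncommon. This also stands, and it limits the weight of the point.

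Third, adjusting for virus would do most of the work and may be planned in an SAP that is not shown. In a two-arm comparison at 50:50, once virus is in the model, the unstratified contrast has only about 1.8% more variance on average. With a 20-point gap it has 1/(1 − 0.20²) = 1.042 times the variance, or 4.2% more. The absence of a covariate from the protocol is therefore no finding. The allocation list is different: the protocol fixes it, and an SAP cannot restratify it afterwards.

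Finally, other baseline factors, such as the stiffness and platelet groups in the study design section, could be proposed as strata on the same argument. That is fair. Virus is preferred here because it defines the two eligible conditions and needs only two lists, not because it has been shown to predict change better.

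**Conclusion.** The point holds as a cheap improvement, not as a defect. All 120 patients go on one unstratified sequence although two conditions known at entry are pooled. A gap of 20 points or more in at least one active arm then has a chance of about 18% to 35% when the minority virus is 20% to 50% of patients, and about 5% at 10%. It would be too strong to call such gaps frequent without knowing the share, or for a single given arm, where the chance is at most about 15.5%. Stratifying does not abolish the gap; it caps it at 2 patients.

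The consequences rest on an assumed virus effect of 0.3 to 0.8 SD. On that range they are modest: well under one standard error for a 20-point gap, and about 1% to 8% in SE at an even mix if virus is left out. Priority is low to moderate.

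**What to change.** In the Block randomization section, specify two allocation lists, one for cured hepatitis C and one for hepatitis B without viral load. Each should consist of blocks of 8 with two places per arm, 1:1:1:1, and the text should state that the order is randomly permuted afresh within every block. Include virus (C or B) as a factor in the between-arm comparisons. If allocation has begun, keep the existing list and add the factor to the analysis only.

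The cost is one additional list and one model term. Arm sizes may range from 28 to 32: about 0.2 power points for a 28 v 32 contrast, and somewhat more in the uncommon case where both compared arms fall short.

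### The 400–450 bp gel rule that selects stool samples for sequencing does not match the nominal product of the stated V4 primers (about 292 bp)

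*Protocol*

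**What the plan says.** All the laboratory steps are in the Protocol, section *Stool sample preparation and microbiota analysis*. The target is the "V4 variable region of bacterial 16S ribosomal RNA gene using PCR primers 515F and 806R". The PCR products are run on an agarose gel, and the rule for going forward is "Samples with bright main strip between 400-450bp will be chosen for further experiments". The products are then mixed and gel-purified. Library preparation comes after that: "Sequencing libraries will be generated using TruSeq DNA PCR-Free sample Preparation Kit (Illumina, USA) following manufacturer's recommendations and index codes will be added". The library is checked on two instruments, with no acceptance threshold given, and then sequenced, when "250 bp paired-end reads will be generated".

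The section gives no expected amplicon length, no primer sequences and no length for any primer tail or barcode. It does not say what happens to a sample whose band lies outside the window.

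The sequencing feeds the first item under *Secondary end points*, "Cirrhosis dysbiosis ratio (CDR), the ratio of autochthonous good bacteria" to pathogenic bacteria. The primary endpoint (section *Primary end point: Fibrosis biomarker*) consists of serum fibrosis markers and the FIB-4 index and does not use the sequencing.

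**The concern.** A gel check before sequencing confirms that the PCR produced the intended fragment, so its size window has to bracket the size of that fragment. Here the window and the primers are given in the same paragraph and do not agree: the fragment implied by the primer labels is well short of the window.

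This is a decision threshold in the protocol, because it determines which samples are carried forward. If the threshold is wrong and the laboratory follows it, valid stool samples do not contribute to the CDR. If the laboratory disregards it, samples are accepted on a criterion that the protocol does not record. In both cases a reader of the results could not tell from the protocol how samples qualified for the first secondary endpoint.

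**Working it through.** **Inputs from the protocol**
- Primer labels: 515 (forward) and 806 (reverse).
- Gel window: 400–450 bp.
- Order of steps: PCR, gel, selection, mixing, gel purification, library preparation with index codes, sequencing.
- Read length: 2 × 250 bp.

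**Assumptions that the protocol does not state**
- The labels are base positions on the 16S gene.
- For the variants below: barcodes of 6–12 nt on each primer, and primers of about 19–20 nt.

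**The plan's own figure.** The 400–450 bp window is stated without derivation. It cannot be reproduced from the primer labels.

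**Nominal product.** Last position − first position + 1 = 806 − 515 + 1 = **292 bp**.

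**Distance to the window**
- Lower edge: 400 − 292 = **108 bp** (400/292 = 1.37 times the nominal span).
- Upper edge: 450 − 292 = **158 bp** (450/292 = 1.54 times).

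**Variants that lengthen the product**

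| Variant | Calculation | Length (bp) | Short of 400 by (bp) |
|---|---|---|---|
| Nominal | 806 − 515 + 1 | 292 | 108 |
| 6 nt barcode on each end | 292 + 2 × 6 | 304 | 96 |
| 8 nt barcode on each end | 292 + 2 × 8 | 308 | 92 |
| 12 nt barcode on each end | 292 + 2 × 12 | 316 | 84 |
| Labels mark inner primer ends (18–19 further nt per side) | 292 + 2 × 18 to 292 + 2 × 19 | 328–330 | 70–72 |
| Inner ends and 12 nt barcodes together | 330 + 2 × 12 | 354 | 46 |

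None reaches 400 bp. Under the nominal reading, tails totalling 108–158 bp would be needed, that is 108/2 = 54 to 158/2 = 79 nt on each primer if split equally. The protocol describes no such tails.

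**Can the order of steps explain the gap?** Not as written. Adapters and index codes belong to the library step, which follows the gel.

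**Does the read length show which figure is right?** The overlap of two 250 bp reads is 500 minus the fragment length: 500 − 292 = 208 bp, 500 − 400 = 100 bp, 500 − 450 = 50 bp. The reads overlap at every one of these sizes, so the read length does not settle it.

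**Samples subject to the rule.** From *Patients and assessments – Study design*, four arms of 30 are sampled at baseline and at six months, and 30 non-cirrhotic comparators once: 120 + 120 + 30 = 270. This is the number to which the rule applies, not an estimate of samples lost.

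**The case against.** The strongest objection is that the contradiction is not wholly internal. The protocol does not say that 515 and 806 are base positions, so the 292 bp rests on a general naming convention. That is fair, and the convention has to be stated as an assumption. The mismatch does not hinge on the exact convention, however: reading the labels as inner primer ends still leaves the product at about 330 bp.

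A second objection concerns the primer construct. PCR products are mixed before index codes are added. If the mixing is across samples, they could be told apart later only if the primers already carried sample-specific sequence, so the product on the gel may be tailed. This also stands. Short barcodes do not close the gap, but long undescribed tails could. A reader might therefore infer that the window *cannot* be met; the documents do not prove that.

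Further inferences go beyond the text:
- **Wrong product is let through.** Nothing in the protocol points to an off-target fragment with a bright band at 400–450 bp.
- **The gel is the only quality check.** Gel purification and a library quality assessment follow, although neither has a stated sample-level threshold.
- **Inclusion becomes a selective judgement after randomisation.** The protocol describes no case-by-case override and no link to treatment arm. If the product is about 292 bp, samples would fail alike in every arm, and a laboratory would probably notice at the first gel.

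Finally, the handling of failed samples may be set out in a statistical analysis plan that is not at hand, so its absence here is not counted as an error.

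**Conclusion.** The point holds as an inconsistency between a stated selection threshold and the stated primers. The nominal 515F/806R product is about 292 bp, or about 304–330 bp with short barcodes or with labels read as inner primer ends, against a required 400–450 bp. The nominal shortfall is 108 bp to the lower edge of the window, and the described sequence of steps does not account for it.

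The consequence is conditional. If the rule is applied literally to product without long primer tails, correctly amplified stool samples in all arms would be excluded from the CDR analysis. The expected result is missing data on a secondary endpoint, or a rule that the laboratory ignores. A reader might go further and infer a bias between arms or the loss of all 270 samples. The documents support neither: the effect would be neutral between arms, and a total loss would require the laboratory to reject every sample without reacting. The primary endpoint is untouched.

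The conclusion assumes that the primer labels are gene positions and that no tails totalling 108–158 bp are present. Confidence is high for the mismatch and moderate for its effect.

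**What to change.** 1. Confirm the primer construct with the laboratory, including any barcode or adapter tail present when the gel is read.
2. State in the stool microbiota section the expected band size, with the tail length shown.
3. Correct whichever item is wrong. If the V4 primers are right and carry no long tails, change the window. If a longer region is really amplified, change the stated region and primers. If long tails explain the window, say so and keep it.
4. Use one primer pair and one window for every sample, at both time points and in the comparator group.

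It would also help to say, here or in the statistical analysis plan, whether a sample that fails the check is re-amplified and when it counts as missing for the CDR.

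The cost is one or two sentences in the laboratory section, with no new samples or patients.

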A stool sample was obtained and dried to obtain a lyophilized extract. To lyophilized faecal samples weighing 1 g, 80% methanol was added. All samples were sonicated for 30 min, refluxed for two hours, and then cooled and filtered. The residue was re-suspended in chloroform/methanol (1:1, v/v), refluxed for one hour, and filtered. The combined extracts were taken to dryness, and re-suspended in 10 ml methanol (MeOH). An aliquot of 1 ml was added with 2 μ l of 1 mg/ml nordeoxycholic acid, and was diluted in 10 ml deionized water and deposited on a 300 mg HLB Oasis column, washed with 10 volumes deionized, 1 volume cyclohexane, and the BAs were then eluted with 5 ml MeOH and were taken to dryness and resuspended in 250 μ l MeOH. Four microliters were injected on liquid chromatography coupled with tandem mass spectrometry (LC-MS/MS) as previously described.

Skin bile acid profile [22]

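### Total stool bile acid, a secondary endpoint, does not exclude UDCA, which two of the four arms take; if the six-month stool is taken on drug, excreted drug can pass for a rise in the patient's own bile acids

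*Protocol*

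**What the plan says.** Under Secondary end points, the second item is "Total stool bile acid, Secondary and primary bile acid ratio". The acids that make up the total are not listed.

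The Study design section sets out the arms. Two contain UDCA: "Group 2: treatment group (ursodeoxy Cholic acid (UDCA) (10mg/kg/day) (n = 30" and "Group 4: treatment group (simvastatin 40mg/day + ursodeoxy Cholic acid (UDCA) (10mg/kg/day) (n = 30". Group 1 is the control and Group 3 takes simvastatin alone.

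The same section says that the faecal, skin and blood measures "were collected at the test base point and six months after treatment". It names the assay: "Analysis of total fecal bile acid: LC-MS/MS system analysis". The section on the fecal bile acid profile describes extraction and column clean-up, then injection for LC-MS/MS by a method given by citation. Neither section says how UDCA is handled in the sum.

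The introduction cites total faecal bile acid of 206.5 µg/100 mg dry stool in healthy controls and 39.0 in advanced cirrhosis. Of ursodeoxycholic acid it says: "acid (UDCA) could enhance the bile synthesis by CYP7A1 altering the gut microbiota population".

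Limitation 1 says: "If post treated human feces contain the trace level of drug, the hypothesis that it is caused by microorganisms alone does not hold". It plans to look for simvastatin and UDCA in post-treatment faeces by TD-ESI, a different method from the LC-MS/MS used for the endpoint.

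**The concern.** UDCA is both a study drug and a member of the class of compounds being summed. Read literally, a total of stool bile acids includes whatever UDCA is in the stool, and only two of the four arms are given it.

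The introduction gives a reason to expect UDCA to change bile acid synthesis, so a rise in the patient's own bile acids is an effect that the trial could reasonably look for. An all-acid total from on-drug stool cannot separate that rise from excreted drug. Because the cited totals are higher in health than in advanced cirrhosis, the artefact would also look like improvement.

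The usual safeguards do not help. The baseline sample precedes dosing, so change from baseline keeps the whole drug contribution. Randomisation does not balance it, because the imbalance is the assigned treatment. Any comparison of an arm with UDCA against an arm without it is exposed. Group 3 versus Group 1 and Group 4 versus Group 2 have no imbalance in UDCA dosing.

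**Working it through.** The protocol gives no expected value, difference or variance for this endpoint, so there is no figure of its own to reproduce. What can be checked is how much excreted UDCA would matter.

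**Inputs from the protocol**
- UDCA dose: 10 mg/kg/day (Study design).
- Total faecal bile acid: 39.0 µg/100 mg dry stool in advanced cirrhosis and 206.5 in healthy controls (introduction).

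**Assumptions not in the documents**
- Body weight 50-80 kg.
- Dry stool 20-50 g/day.
- The share of the dose recovered in stool as UDCA is unknown, so the calculation solves for it.

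**Step 1: daily dose.** Dose = 10 mg/kg × weight, so 500 mg at 50 kg and 800 mg at 80 kg.

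**Step 2: daily bile acid output without the drug.** Since 1 µg/100 mg = 0.01 mg/g, output = concentration × dry stool mass.
- At 39.0 (0.390 mg/g): 0.390 × 20 = 7.8 mg; 0.390 × 50 = 19.5 mg.
- At 206.5 (2.065 mg/g): 2.065 × 20 = 41.3 mg; 2.065 × 50 = 103.25 mg.

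**Step 3: recovery that doubles the total.** Threshold = output / dose.

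| Starting total (µg/100 mg) | Lowest (80 kg, 20 g) | Central (60 kg, 30 g) | Highest (50 kg, 50 g) |
|---|---|---|---|
| 39.0 | 7.8/800 = 0.98% | 11.7/600 = 1.95% | 19.5/500 = 3.9% |
| 206.5 | 41.3/800 = 5.16% | 61.95/600 = 10.3% | 103.25/500 = 20.65% |

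**Step 4: sensitivity to the stool mass assumption.** With dry stool capped at 40 g/day, the upper limits become 15.6/500 = 3.1% and 82.6/500 = 16.5%.

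Doubling is only a convenient yardstick. The protocol gives no level for the patients to be enrolled. Hepatic decompensation is an exclusion, so their starting level may lie between the two cited values, and the threshold with it.

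**Step 5: timing.** The phrase "were collected at the test base point and six months after treatment" has two readings. One is the end of six months on treatment, in which case the calculation applies. The other is six months after the last dose, in which case the direct contribution of drug would be expected to be small. The protocol does not decide between them.

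**The case against.** The best defence is that the list of acids summed into a laboratory variable is ordinary detail for an SAP or laboratory manual. The SAP is not at hand, and the protocol gives its LC-MS/MS method by citation. The word total names no analytes, and if UDCA is reported separately it can be removed later with no data lost. Much of this stands, and it keeps the point small. It does not dispose of it: the protocol names an endpoint that, followed as worded on on-drug stool, would count study drug as outcome.

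It can also be said that an all-acid total is a sensible measure of what the gut is exposed to, since the introduction treats bile acids as acting on the microbiota and on receptors. That is fair, and it is why the all-acid total should still be reported. It does not make that total a measure of the patient's own bile acids.

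Some stronger readings are tempting but unsupported:
- A reader might infer from the work-up, where "the BAs were then eluted with 5 ml MeOH and were taken to dryness", that UDCA is necessarily counted. That step is clean-up before injection and does not show which acids are later quantified or summed.
- A reader might take Limitation 1 as the sponsor conceding this flaw. It most naturally concerns the transplant of human faeces into mice, which the introduction describes and Limitation 2 continues. It shows only that drug may be expected in post-treatment stool. Its TD-ESI check detects UDCA and does not take it out of this endpoint.
- A reader might infer that the comparison will be biased. The documents give neither the faecal recovery nor a clear sampling time, so they show a possibility and not a certainty.

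**Conclusion.** The point holds conditionally and is minor. As worded, the total does not exclude a bile acid given to two of the four arms. If the six-month stool is taken on drug, excreted UDCA can raise the total in those arms and be mistaken for a rise in the patient's own bile acids.

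The thresholds (about 1.0-3.9% of the dose from 39.0 µg/100 mg, about 5.2-20.7% from 206.5) rest on assumed weight and stool mass. They say how little or how much recovered drug would matter, not how much will be recovered. If the stool is taken well after the last dose, the problem largely falls away.

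The reach is one component of one secondary endpoint. The primary fibrosis markers are unaffected, and the cirrhosis dysbiosis ratio and the cytokines do not count UDCA. A reader might infer that the trial's main conclusions are at risk; nothing in the protocol supports that.

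**What to change.** 1. State whether the six-month stool is collected on drug or after the last dose, and how long after. This comes first, because it decides whether the problem arises.
2. Define the endpoint as total stool bile acid excluding UDCA and its conjugates, identically in all four arms, from the planned LC-MS/MS profile.
3. Report UDCA itself and the all-acid total descriptively by arm.

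The cost is a change of endpoint wording and one more derived variable. No new assay is needed provided that the LC-MS/MS profile reports UDCA separately; the protocol does not say, so the laboratory should confirm it. The definition should be fixed before the data are seen.

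There are two downsides. The redefined endpoint is less directly comparable with the cited 39.0 and 206.5, which reporting the all-acid total offsets. Any UDCA that is converted to other bile acids stays in the endpoint, so the separation is incomplete; the documents give no figure for that share.
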